4.4 Treatment of Subjects

The amount of time from patient admission to the emergency department until they are seen by an OHNS resident may be variable due to extraneous circumstances. Upon consult by OHNS if the patient meets the criteria for the study, informed consent will be obtained by a member of the research team (not the direct care team). They will have an opportunity to ask questions and sign the consent form.

a. Participants will be randomized using a sealed envelope system to either experimental or control group

b. Group A receives traditional nasal packing by a trained OHNS resident (merocel gauze)

Group B receives treatment using 5 mL of Floseal Hemostatic Matrix by a trained OHNS resident

c. Both Groups are followed to observe the primary endpoint of hemostasis (end of bleeding)

d. If hemostasis is not promptly achieved (as determined by the direct care team) than additional measures will be taken to arrest bleeding just as they would in any other non-study situation

e. Hospital care or discharge continues as normal

f. Patients are telephoned or visited as inpatients 48 hours later to complete the comfort questionnaire

We will have extra follow-up with these patients to observe the effects of our treatment on patient comfort and allow for the opportunity of a study debrief. This will occur two days following their treatment and should last no more than five minutes over the telephone.

4.5 Medication

All other medication required by the patient or medications they are already taking will be continued and will not interfere with the progression of this study.

5 Assessment of Efficacy

5.1 Efficacy Parameters

Efficacy of the Floseal Hemostatic Matrix will be determined by observing whether patients receiving either the Floseal or control treatment require additional measures to abort bleeding. Our primary endpoint is hemostasis, however if hemostasis is not adequately achieved, as determined by the OHNS resident providing direct care, than additional measures will be taken to abort bleeding and this will signify our primary endpoint.

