Management of Persistent Epistaxis Using Floseal Hemostatic Matrix

PROTOCOL IDENTIFYING NUMBER 001

PROTOCOL VERSION DATE June 8, 2015

GENERAL INFORMATION

Name and title of the investigators and sub-investigators responsible for the trial with address and phone numbers

[name] [name]

[name] [contact]

[name]

[name] [contact]

[name] BSc.

[name] [contact] [contact]

| Title | Management of Persistent Epistaxis using Floseal Hemostatic Matrix |
|--|---|
| Short Title | Floseal Epistaxis Study |
| Protocol Number | 001 |
| Phase | Phase 4 Clinical Trial |
| Methodology | Randomized open-label Trial |
| Study Duration | 1 Year |
| Study Center(s) | Single-Center, University of Alberta |
| Objectives | We wish to observe the effectiveness of Floseal Hemostatic Matrix in aborting persistent epistaxis with the end of bleeding being our primary outcome. We also wish to include measures of patient comfort and cost analysis of epistaxis treatment. |
| Number of Subjects | 60 |
| Diagnosis and Main Inclusion Criteria | Adult patients presenting for Otolaryngology Head and Neck Surgery consult in the Emergency Department with persistent epistaxis. |
| Study Product, Dose, | Floseal Hemostatic Matrix, 5mL |
| Duration of administration | 30 Minutes |
| Reference therapy | Standard nasal packing using gauze by a trained Otolaryngology resident |
| Statistical Methodology | This study is powered based on a non-inferiority analysis to compare the efficacy of Floseal at achieving hemostasis. We will perform standard chi-square statistical analysis to determine the significance of these outcomes. |

Study Summary

Table of Contents

| 1 | | BACKGROUND | .1 |
|----|-----|---|---------------------|
| | 1.1 | INVESTIGATIONAL AGENT | .1 |
| | 1.2 | PRECLINICAL DATA | .1 |
| | 1.3 | Risk/Benefits | .1 |
| | 1.4 | DOSE RATIONALE | .1 |
| | 1.5 | TRIAL CONDUCT | .1 |
| | 1.0 | POPULATION. | .2 |
| | 1./ | LII EKA I UKE | .2 |
| 2 | | TRIAL OBJECTIVES | .2 |
| 3 | | TRIAL DESIGN | .2 |
| | 3.1 | PRIMARY STUDY ENDPOINTS/SECONDARY ENDPOINTS | .2 |
| | 3.2 | Study Design/Type | .2 |
| | 3.3 | RANDOMIZATION | .3 |
| | 3.4 | TRIAL TREATMENT | .3 |
| | 3.5 | DURATION | .3 |
| | 3.6 | DISCONTINUATION | .4 |
| | 3.7 | DATA IDENTIFICATION | .4 |

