3.1 Primary Study Endpoints/Secondary Endpoints

The primary endpoint of this study will be when hemostasis is achieved and there is no longer any active bleeding from the nasal cavity. Our secondary endpoint will be two days following the intervention when we obtain the telephone questionnaire results from the patients about pain level and comfort of the treatment.

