3.2 Study Design/Type

This study will be a prospective randomized, open-label clinical trial.

- 1. Otolaryngology Service consulted for persistent epistaxis by Emergency department
- 2. Otolaryngology resident determines whether patient meets inclusion/exclusion criteria for the study
- 3. Informed Consent is obtained and participants are given a chance to ask questions
- 4. Participants will be randomized using a sealed envelope system to either experimental or control group
- 5. Group A receives traditional nasal packing

Group B receives treatment using FloSeal Hemostatic Matrix

- 6. Both Groups are followed to observe the primary endpoint of hemostasis (end of bleeding)
- 7. Hospital care or discharge continues as normal
- 8. Patients are telephoned or visited as inpatients 48 hours later to complete the comfort questionnaire

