7.1 Statistical Methods

As this study is comparing a single experimental group to a control group we will use a standard statistical analysis to compare both the primary outcome of hemostasis and the secondary outcome results of the pain and comfort questionnaire. This is a non-inferiority study and has been powered as such. We will use a chi-square test to determine significance of any difference between the treatment and control group.

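### The primary endpoint has no single rule for scoring a patient who needs additional measures: 3.1 and 5.1 do not agree, 5.1 is unclear within itself, and the SAP does not settle it

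*Protocol*

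**What the plan says.** The protocol's Study Summary describes the aim as stopping persistent epistaxis with Floseal, "with the end of bleeding being our primary outcome". Section 3.1 says: "The primary endpoint of this study will be when hemostasis is achieved and there is no longer any active bleeding from the nasal cavity". Section 3.2 (step 6) and section 4.4 (item c) repeat hemostasis, glossed as the end of bleeding, as the primary endpoint. None of the four says how a patient who needed more than the assigned treatment is scored.

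Section 4.4 (item d) covers care when hemostasis is not prompt: "additional measures will be taken to arrest bleeding just as they would in any other non-study situation". It gives no scoring rule.

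Section 5.1 opens with a different criterion. Efficacy "will be determined by observing whether patients receiving either the Floseal or control treatment require additional measures to abort bleeding". It then names hemostasis as the primary endpoint and says that, where the resident judges hemostasis inadequate, "than additional measures will be taken to abort bleeding and this will signify our primary endpoint".

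Section 7.1 plans to "compare both the primary outcome of hemostasis and the secondary outcome results of the pain and comfort questionnaire". The SAP (Sample Size) assumes about 93% success in each arm, drawing on literature on anterior packing, and does not define success.

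On quantity, section 4.4 (item b) says "Group B receives treatment using 5 mL of Floseal Hemostatic Matrix by a trained OHNS resident", while section 3.4 allows the amount of Floseal to vary. No packing quantity is stated.

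**The concern.** Take a patient whose bleeding continues after the assigned treatment and then stops after further measures. Under the first sentence of 5.1 this patient is a failure. Under the words of 3.1 the patient has reached hemostasis. The last clause of 5.1 attaches the term primary endpoint to the taking of additional measures, so the same term appears to mark both hemostasis and its absence.

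The choice matters more than usual because this is a non-inferiority trial. Counting rescued patients as hemostasis raises both arms toward 100% and pulls them together. When Floseal is truly worse, that favors a finding of non-inferiority. The SAP would prefer Floseal on comfort and cost once hemostasis is shown to be non-inferior, so a false pass would change the recommendation. The resident who judges whether hemostasis is adequate is unblinded (3.3, 5.1). At 13 per arm, reclassifying one patient moves an arm by 1/13 = 7.7 points.

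The same gap covers repeats of the assigned product: no section says whether a second Floseal set or a re-pack is an additional measure.

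**Working it through.** **Step 1. The texts side by side.**

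| Place | What it gives | Rescued patient who stops bleeding |
|---|---|---|
| Study Summary | End of bleeding, in a sentence about Floseal aborting it | Not stated |
| Section 2 | Floseal's own ability to abort bleeding | Suggests failure |
| 3.1; 3.2 step 6; 4.4c | Hemostasis, end of bleeding | Not stated; the words allow success |
| 4.4d | Rescue when hemostasis is not prompt | Suggests failure |
| 5.1, first sentence | Need for additional measures | Failure |
| 5.1, last clause | Taking those measures signifies the endpoint | Unclear |
| 7.1 | Compares hemostasis | Not stated |
| SAP | Success, 93%, from packing literature | Not stated; the rate fits failure |

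**Step 2. Reproduce the SAP's sample size.** Inputs: success 93% in both arms, margin 25 points, alpha 5%, power 80%.

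n = 2 × 0.93 × 0.07 × (1.645 + 0.842)² / 0.25² = 12.9, so 13 per arm and 26 in total, as the SAP states. The match needs a one-sided 5% level; one-sided 2.5% gives 17 per arm.

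**Step 3. Effect of the scoring on the true difference.** Let pF and pC be success with the assigned treatment alone, and r the share of first failures that rescue stops. r is assumed equal in both arms; no document gives it. If rescued patients count as hemostasis, the arms become pF + (1 - pF)r and pC + (1 - pC)r. The difference is then (pF - pC)(1 - r), at any sample size and with any interval method.

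For pF = 68% and pC = 93%, a shortfall equal to the SAP margin:
- r = 50%: 84.0% v 96.5%, difference 12.5 points
- r = 80%: 93.6% v 98.6%, difference 5 points
- r = 90%: 96.8% v 99.3%, difference 2.5 points

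**Step 4. Chance of declaring non-inferiority.** Exact enumeration over two independent binomials. Non-inferiority is declared when the one-sided 95% lower bound for Floseal minus packing lies above minus the margin. The bound is an assumption: the SAP names Fisher's exact test and 7.1 a chi-square test, and neither states a bound. True rates with the assigned treatment alone are 68% v 93%.

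| Scoring of rescue | 13 per arm, margin 25: Newcombe / Wald | 30 per arm, margin 5: Newcombe / Wald |
|---|---|---|
| Failure | 6.0% / 7.6% | 0% / 0% |
| Success, r = 50% | 22% / 38% | below 1% / 1% |
| Success, r = 80% | 49% / 80% | below 1% / 14% |
| Success, r = 90% | 68% / 94% | below 1% / 38% |

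The first column of results uses the SAP's design, the second the protocol's (7.2, 7.3). The low Newcombe figures in the second column reflect a design with little chance of passing at all. With both arms truly at 93%, 30 per arm, a 5-point margin and rescue scored as failure, Newcombe passes in only 12.7% of trials.

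**The case against.** A reader might infer that the plan has adopted an endpoint of hemostasis by any means, and that it therefore hides an inferior Floseal. The documents do not support this. No section says by any means; 3.1, 3.2 and 4.4c are silent on means. The Study Summary and section 2 tie the outcome to Floseal's own effect. Section 4.4d starts rescue because prompt hemostasis has not been achieved, and 5.1 because it is inadequate, so in both a rescued patient is one in whom the assigned treatment fell short. Section 5.1 is the only section that says how efficacy is judged, and its first sentence scores the need for more measures. The SAP's 93%, taken from work on packing, fits that scoring.

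The last clause of 5.1 also has a milder reading. Section 3.1 uses endpoint partly as a time point: its secondary endpoint is two days after treatment. On that usage the clause may only mark when observation ends for a patient who needed rescue.

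These arguments stand, and they settle the likely intent. They do not supply the missing rule. If the clause marks a time, it still does not say how that patient enters the comparison in 7.1, and a chi-square or Fisher test needs each patient scored one way or the other.

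The calculations are also conditional. They need the less likely reading, an assumed r and an assumed bound, and at the protocol's own margin and sample size the Newcombe result hardly moves. That limits the claim about size. The inconsistency does not depend on it.

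It would also go too far to say that a second Floseal set must be a failure. Section 4.4b names 5 mL, but 3.4 allows the amount to vary, so the documents leave that choice open.

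**Conclusion.** The point holds as an inconsistency in the definition of the primary endpoint. The probable intent is that needing additional measures is a failure, but the text also permits rescued patients to be counted as hemostasis, and neither 7.1 nor the SAP rules that out.

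If rescued patients were so counted, a Floseal shortfall of 25 points would pass the SAP's criterion in 22-38% of trials at r = 50%, 49-80% at r = 80% and 68-94% at r = 90%, against 6-8% when rescue is a failure. This rests on the SAP's 13 per arm and 25-point margin, an assumed one-sided 95% bound, and an assumed r equal in both arms. At the protocol's 30 per arm and 5% margin, Newcombe stays below 1% under either scoring, and Wald rises from 0% to 1%, 14% and 38%. The definition should be corrected. The figures show what it could cost if left open and do not predict how the trial will be scored.

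**What to change.** In 5.1, replace the closing words on what signifies the primary endpoint with: *this will be scored as treatment failure*. Use one definition in the Study Summary, 3.1, 3.2, 4.4c, 5.1 and the SAP: *Success is hemostasis with the assigned treatment alone; any patient who receives additional measures to stop bleeding is a failure in both arms.*

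State in advance, with the same rule for both arms, whether a second Floseal set or a re-pack is an additional measure. Given 3.4, that choice is the sponsor's. Report the other choice as a sensitivity analysis, and report eventual hemostasis by any means descriptively only.

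The cost is an ethics board amendment and, if the data form lacks them, entries for sets, packs and further measures (the form is not in the reviewed text). If repeats are scored as failures, observed Floseal success may fall and power with it. For example, if Floseal fell to an assumed 85% against 93%, power at 13 per arm and a 25-point margin would drop from 81% to 47% (Wald) or from 66% to 36% (Newcombe). That should be weighed before the rule on repeats is fixed. Patient care and randomization do not change.

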5.2 Method and Timing

The research team will review the data obtained following each patient enrolled in the study to ensure that the protocol is being followed appropriately and that the primary and secondary endpoints are being appropriately recorded.

6 Assessment of Safety

6.1 Safety Parameters

Patient safety throughout this trial will be monitored by both the direct care team and the research team. The direct care team will be able to contact the research team at any time to report and concerns that may arise regarding patient safety. The research team will also periodically (2-3 weeks) check in with the direct care team to ask about any concerns that they might have.

6.2 Method and Timing

Assessing safety will be the responsibility of the direct care team following the enrollment of each patient in the study. Safety concerns will be brought to the attention of the research team immediately if they are to arise. The research team will seek out concerns on a 2-3 week basis with the direct care team. Concerns will be recorded and

kept securely with the rest of the trial data on an encrypted computer in the research office.

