1.2 Preclinical Data

Floseal has been previously shown to achieve hemostasis more effectively than traditional methods in a number of clinical settings. These include cardiac surgery, spinal surgery and topical bleeding. Gel like hemostatic agents have additional advantages such as ease of use, conformity to irregular surfaces and their bio absorbable properties eliminate the need for removal. A prospective clinical trial using 10 patients at the University of Alberta has already been conducted, however it was not a randomized clinical trial and did not look at outcomes in addition to hemostasis. We wish to expand upon this knowledge in the context of epistaxis in this study.

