4.3 Subject Withdrawal

Patients will be undergoing all aspects of the study under the supervision of a physician or research coordinator and will therefor be encouraged to express any concerns they have so they can be addressed as promptly as possible. We will minimize risk by providing the physicians involved with the most training possible to ensure placement of the treatment is done as easily and accurately as it can be. Patients who wish to withdraw from the study will be able to do so at any time and will be informed of this upon obtaining consent for the study. They will be instructed to speak with any member of the direct care or research team to withdraw him or herself from the study. Patients will not be replaced as this study has a rolling enrollment and we will continue until we acquire the proper number of participants. Data from the withdrawn participants will be discarded, however we will keep the record of the patient themselves and follow-up with them as we would any other patient in the study (if they are willing) to monitor for any adverse events and ensure patient safety.

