6.4 Adverse Event Follow-up

The direct care team will report any adverse events to the research team. The research team will follow-up with the patients in person or via telephone for the duration of treatment or until the adverse event has resolved. This study will not interfere with the normal care and treatment of these patients either before or after participation in the study.

7 Statistical Plan

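### The only adverse-event detection route the protocol spells out runs through the unblinded care team; the one scheduled patient contact is described as comfort and debrief, so harms after discharge may be missed

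*Protocol*

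**What the plan says.** **Who looks for harms.** Protocol section 6.2: "Assessing safety will be the responsibility of the direct care team following the enrollment of each patient in the study". Section 6.4 sets the reporting route: "The direct care team will report any adverse events to the research team". Section 6.2 gives the research team's own search: "The research team will seek out concerns on a 2-3 week basis with the direct care team". Section 3.3 says that neither the care team nor the patient can be blinded.

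**What happens to the patient.** After treatment, usual hospital care or discharge follows (3.2 item 7, 4.4e). The one scheduled contact is a call or inpatient visit at 48 hours to complete the comfort questionnaire (3.2 item 8, 4.4f). Section 4.4 gives its purpose as "to observe the effects of our treatment on patient comfort and allow for the opportunity of a study debrief". Section 3.5 leaves the telephone survey to the patient's choice.

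**What points towards wider follow-up.** Section 6.1: "Patient safety throughout this trial will be monitored by both the direct care team and the research team". Section 6.4 has the research team follow patients in person or by telephone "for the duration of treatment or until the adverse event has resolved". Section 4.3 says of withdrawn patients that the team will "follow-up with them as we would any other patient in the study", if they are willing, to monitor for adverse events.

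**What the SAP says.** It names no adverse-event analysis. It makes Floseal a preferred option if hemostasis is shown to be non-inferior.

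**The concern.** A harm that appears after discharge enters the record only if the patient returns to the care team, or raises it unprompted in a voluntary call made for another purpose. No visible section has anyone ask a discharged patient about harms.

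This matters for two reasons. First, the case for Floseal is non-inferior hemostasis plus better comfort and possibly lower cost. That case takes for granted that its harms are no worse, and a low event count supports this only if someone looked. Second, sections 6.3 and 7.4 rely on adverse events reaching the research team so that they can be reported to the ethics board or lead to termination. Neither provision works for events that nobody elicits.

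A further possibility is unequal capture. Section 1.2 says of gel agents that "their bio absorbable properties eliminate the need for removal", which implies that packing does need removal. If packed patients came back for removal and Floseal patients did not, packed patients would have one more occasion on which an event could be noticed.

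**Working it through.** The documents state no safety figure, so there is none to reproduce. The check is first a comparison of sections, then an illustration of size.

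**Step 1: what each section specifies**

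| Protocol section | Who is asked or observed | When | Adverse-event questions |
|---|---|---|---|
| 6.1 | Both teams monitor; the mechanism given is care team to research team, plus check-ins with the care team | every 2-3 weeks | none stated |
| 6.2 | Care team assesses; research team asks the care team | after each enrollment; every 2-3 weeks | none stated |
| 6.4 | Care team reports; research team then follows patients | to end of treatment or resolution of the event | none stated |
| 4.3 | Withdrawn patients, on the same footing as all others | not stated | none stated |
| 3.2 item 8, 4.4f | Every patient | 48 hours | comfort questionnaire; items not visible |

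Sections 4.3 and 6.1 presuppose patient-level safety follow-up. Sections 6.2 and 6.4 do not supply it: follow-up in 6.4 comes directly after care-team reporting and can end when the event resolves, so it reads as following events already reported.

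**Step 2: loss of events, same in both arms**

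Inputs: n = 30 per arm (protocol 7.2) or 13 per arm (SAP, Sample Size). The true event risk r and the share captured c are assumptions, as neither document gives them. With independent patients and at most one counted event each:

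P(at least one event recorded in an arm) = 1 − (1 − r·c)^n

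Example: r = 0.10, c = 0.50, n = 30 gives 1 − 0.95^30 = 0.785.

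| r | n | c = 100% | c = 50% | c = 25% |
|---|---|---|---|---|
| 5% | 30 | 0.785 | 0.532 | 0.314 |
| 10% | 30 | 0.958 | 0.785 | 0.532 |
| 20% | 30 | 0.999 | 0.958 | 0.785 |
| 5% | 13 | 0.487 | 0.280 | 0.151 |
| 10% | 13 | 0.746 | 0.487 | 0.280 |
| 20% | 13 | 0.945 | 0.746 | 0.487 |

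This loss needs no difference between the arms.

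**Step 3: distortion if capture differed**

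Spurious difference = r × (c_packing − c_Floseal), with the same true risk in both arms. Packing capture is assumed to be 90%.

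| r | Floseal capture 90% | 70% | 50% | 30% |
|---|---|---|---|---|
| 5% | 0 points | 1 | 2 | 3 |
| 10% | 0 points | 2 | 4 | 6 |
| 20% | 0 points | 4 | 8 | 12 |

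One worked case: r = 15%, capture 90% against 40%. Observed rates are 0.15 × 0.9 = 13.5% and 0.15 × 0.4 = 6.0%. The chance of recording no Floseal event is (1 − 0.06)^13 = 0.447 against (1 − 0.15)^13 = 0.121 with full capture. For n = 30 it is 0.94^30 = 0.156 against 0.85^30 = 0.008.

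These figures show what unequal capture would do, not that it occurs. If capture were better in the Floseal arm, the sign would reverse.

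**The case against.** The strongest reply is that the protocol does not confine safety to the care team. Section 6.1 names both teams, 6.4 gives the research team direct contact with patients, and 4.3 implies that ordinary participants are followed for adverse events. Sections 3.6 and 4.3 also encourage patients to voice concerns, and the 48-hour contact includes a debrief at which a harm could be raised. This stands to the extent that the care-team route is not stated to be exclusive: it is the only one spelled out. None of these sections gives a time, a method or a question for detecting events in discharged patients.

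The questionnaire items and consent pages were not visible in this review, so an adverse-event item or an instruction to report problems may already exist. This also stands, and the fix is conditional on it.

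Three stronger readings are tempting, but the documents do not support them:

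- **That harms are in fact missed unequally, in favour of Floseal.** No section describes a removal visit: whether it happens after discharge, who does it, or whether events are recorded there. Some patients are still inpatients at 48 hours.
- **That the safety window is shorter for Floseal,** by reading the study summary's 30 minutes of administration into the treatment duration in 6.4. Section 3.5 discusses duration for both arms together, with time to hemostasis of at most a few hours, and sets no arm-specific window. Section 6.4 reads as follow-up of reported events.
- **That a planned analysis is biased.** Neither document plans a comparison of adverse events between arms.

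**Conclusion.** The concern holds as a gap in safety capture. The protocol specifies detection through unblinded clinicians, and the visible text requires no standard adverse-event question to any patient after discharge. Harms after discharge may be missed in either arm. Sections 4.3 and 6.1 need to be reconciled with 6.2 and 6.4.

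The size cannot be derived from the documents. Over assumed risks of 5-20%, capturing half of events instead of all lowers the chance of seeing any event in an arm of 13 by about 0.20 to 0.26 (for example 0.746 − 0.487 = 0.259 at 10%). In an arm of 30 the loss is about 0.04 to 0.25. A between-arm distortion is possible but not shown: its direction is unknown and it is zero under equal capture.

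The change is worth making because it is cheap and does not depend on whether capture differs by arm. The conclusion rests on the stated purpose of the 48-hour contact and on the questionnaire not already asking about harms.

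**What to change.** 1. In protocol 3.2 item 8, 4.4f and 6.2, have the research team ask every patient in both arms the same short questions at the existing 48-hour contact: any new symptom, any return to care, any event at the nose, and one open question. This is unnecessary if the questionnaire already contains them; in that case, say so in section 6.
2. Record the answers separately from the comfort items.
3. Report all events by arm with their source (elicited at 48 hours or reported by the care team), and the number of patients per arm not reached. Do not restrict the arm comparison to elicited events: the call is voluntary, and doing so would discard events seen by the care team and those in patients who decline.
4. Reconcile 4.3 and 6.1 with 6.2 and 6.4, stating who follows patients for adverse events and how.

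Cost: protocol wording and a few questions in a contact that already takes place, with no new visit. The call runs slightly longer, and more minor events will need reporting. Events that first appear after 48 hours would still depend on the care team, and the reports should say so.
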